Duration of Therapy	Patients will receive treatment for approximately 21 weeks.
Duration of Follow up	Follow-up visits will occur at 3, 6, & 12 months (+/- 2 weeks) post End of Treatment visit. Survival follow-up information may be collected via telephone calls and/or at clinic visits every 3 months for 12 months.
Duration of study	The study will reach completion 3-4 years from the time the study opens to accrual.
Study Drugs	Vismodegib capsules (150 mg QD PO) will be taken orally (whole). Patients will be instructed to swallow one capsule once a day (preferably at the same time each day) 7 days/week, with or without food, with about 1 cup (240 mL) of water. Capsules must be swallowed whole; they must not be opened, chewed, broken, or crushed under any circumstances.
Safety Assessments	
The study will use the CTCAE v 4.0 for reporting of non-hematologic adverse events and modified criteria for hematologic adverse events. Safety assessments will consist of monitoring and reporting adverse events (AEs) and serious adverse events (SAEs) that are considered related to vismodegib, all events of death, and any study specific issue of concern.
 
The study period during which all AEs and SAEs must be reported begins after informed consent is obtained and initiation of study treatment and ends 12 months following the last administration of study treatment or study discontinuation/termination, whichever is earlier.

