5.3 Dose Modifications and Dosing Delays

There are no planned dose reductions of vismodegib.

Treatment with vismodegib may be interrupted for up to 4 weeks for evaluation of an intolerable toxicity finding. In addition, treatment with vismodegib may be interrupted for up to 4 weeks if a patient becomes temporarily unable to swallow capsules or is in need of an unrelated surgical procedure which does not require disenrollment from the study. Any other proposed reasons for interruption of treatment should be discussed in advance with the Principal Investigator. If the patient resumes drug, administration will start at the point in the protocol at which was interrupted and the total durations of days of drug given to the patient should equal those specified in the protocol.

Radiation therapy should not be halted if at all possible and any radiation delays are to be stringently avoided, even if drug administration is interrupted. If radiation therapy treatments are interrupted for any reason, including holidays or mechanical breakdown, the missed treatments are to be added to the end of the treatment course, such that the total radiation dosage and days of radiation therapy given to the patient should equal those specified in the protocol.

If either vismodegib or radiation treatment has been held for more than 28 days to allow for resolution of an adverse event, the treating physician should contact the Study Chair to review the subject's condition prior to resuming the patient's treatment, except for delays due to hypertension. As a patient progresses from one treatment to another (i.e., pre-radiation therapy, radiation therapy, post radiation therapy), the patient should remain at the SAME DOSE LEVEL.

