6.1.3 End-of-Treatment Study Procedures

To be completed within 8 – 12 weeks of the last dose of study drug.

- Physical examination including weight
- Vital signs
- Performance status
- Evaluation of adverse events
- Concomitant medications
- Skindex-16 survey
- Laboratory assessments
 - Hematology
 - Serum chemistries
- Urine or serum pregnancy tests within 4 weeks after completion of radiation therapy - if a woman of childbearing age
- Disease assessment
- Imaging (CT or MRI) of head and neck for tumor assessment
- CT chest or chest x-ray – if clinically indicated
- For externally visible tumors
 - Bidimensional measurements of externally visible tumor dimension
 - Digital photography of target lesion(s)
 - Description of the lesion
 - Tumor biopsy – as needed to confirm progression

If biopsy results are confirmatory of persistent cancer, the patient may be offered salvage surgery as indicated. This would result in discontinuation from the study. Post-salvage follow-up may be conducted by UCSF investigators with separate consent by the patient.

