6.1.4 Post-treatment/Follow Up Visits

Patients will be followed at 3, 6, and 12 months (+/- 2 weeks) after the End of Treatment visit or until disease progression. The following procedures will be performed at the Follow-Up Visit(s):

- Evaluation of clinical response or deterioration
- Physical examination including weight
- Vital signs
- Performance Status
- Evaluation of adverse events
- Concomitant medications
- Skindex-16 survey
- Laboratory assessments
 - Hematology

- Serum chemistries
- Urine or serum pregnancy tests - if a woman of childbearing age – at 3 and 6 month visits only
- Disease assessment
- Imaging (CT or MRI) of head and neck for tumor assessment
- CT chest or chest x-ray – if clinically indicated
- For externally visible tumors
 - Bidimensional measurements of externally visible tumor dimension
 - Digital photography of target lesion(s)
 - Description of the lesion
 - Tumor biopsy - to confirm progression

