Chest x-ray, CT Chest, or PET/CT ^{6,10}	X				X								X	X

- Follow-up visits will occur at 3, 6, & 12 months (+/- 2 weeks) post EOT. Patients with documented disease progression within the irradiated PTV will be removed from study treatment. Survival follow-up information may be collected via telephone calls and/or at clinic visits every 3 months for 12 months.
- The reporting period for adverse events (AEs) and serious adverse events (SAEs) will begin at the time of enrollment and continues until 90 days after the last dose of vismodegib. During screening, only SAEs related to protocol-mandated procedures should be reported. At the end of the study period, any patient with an ongoing AE or SAE will be followed until the event resolves, the investigator assesses the event as stable, or the patient is lost to follow-up.
- A complete physical exam includes evaluation of the head, eyes, ears, nose and throat; cardiovascular, dermatological, musculoskeletal, respiratory, gastrointestinal, and neurological systems. Exam includes height (at screening only) and weight.
- Vital signs include pulse, systolic and diastolic blood pressure while the patient is in a seated position, respiratory rate, and temperature.
- For externally visible tumors. Can be done up to 180 days prior to day 1. Additional biopsy after screening will only be to confirm progression.
- Dental evaluation, fine needle biopsy, Brain MRI, and PET/CT are highly recommended but not required at screening.
- Hematology consists of hemoglobin, hematocrit, platelet count, red blood cell (RBC) count, white blood cell (WBC) count, and percent or absolute differential count (neutrophils, eosinophils, lymphocytes, monocytes, basophils, and other cells).
- Serum chemistry includes glucose, blood urea nitrogen (BUN), creatinine, sodium, potassium, magnesium, chloride, bicarbonate (if routinely performed on venous blood samples), calcium, total protein, albumin, total bilirubin, alkaline phosphatase, AST, and ALT, and as clinically indicated; LDH, and phosphorus
- The CT scan with contrast or an MRI with gadolinium must be done unless medically contraindicated. The MRI or CT scan must encompass the skull base and/or upper mediastinum if those areas are involved. If locally advanced BCC lesions with a RECIST-measurable component are identified, the same imaging modality used at baseline must be used throughout the study.

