8.2 Study Endpoints

Primary Endpoint:

- The proportion of patients with local-regional control at 12 months from protocol therapy completion, defined as complete or partial response, with absence of PD (see section 7.2) within the irradiated PTV.

Secondary Endpoints:

- Estimate of the probability of PFS and OS 12 months after protocol therapy completion. PFS is measured until disease recurrence or death due to any cause, whichever occurs first.
- Number and attribution of all adverse events (including vital signs, physical findings, and clinical laboratory results, CTCAE, v 4.0) in patients who receive any amount of study drug and radiation therapy.
- For each toxicity, the maximum occurring grade will be tabulated for each patient. The results will be summarized by toxicities observed during vismodegib treatment alone, during concurrent vismodegib with radiation therapy, for 3 months immediately following the completion of protocol therapy and for up to 12 months after completion of protocol therapy. The focus will be on the proportion of patients experiencing \geq grade 3 toxicity during each of these intervals.
- Proportion of patients experiencing Grade 4-5 adverse events assessed to be definitely, probably, or possibly related to the induction or concurrent treatment components of the protocol regimen (that is not definitely related to disease progression).
- Proportion of patients discontinuing treatment due to toxicity during the concurrent administration of vismodegib and radiation therapy. For this endpoint, discontinuation is defined as $<$ 75% of planned radiation therapy delivered.
- Response rate per RECIST criteria in patients who complete initial combined therapy of the primary site and regionally involved areas in subjects with measurable disease prior to initiation of therapy at 3 months after completion of protocol therapy.
- Proportion of patients with a decrease of BCC within the irradiated PTV after completing all protocol therapy to estimate clinical response to vismodegib and radiation therapy.

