8.3 Determination of Sample Size and Accrual Rate

8.3.1 Sample Size and Power Estimate

The sample size for this single-arm phase II study is based upon the anticipated degree of improvement in the primary clinical hypothesis (i.e. local-regional control rate) at 12 months after completing all protocol treatment. The null hypothesis is that 60% of patients treated may achieve local-regional control after treatment on the study. Patients treated for advanced-stage

nonmelanomatous skin cancers typically achieve 50-60% local-regional control with radiation therapy alone. The alternative hypothesis is that 80% of the patients will obtain local-regional control at 12 months from the end of protocol therapy. This goal for local-regional control is justifiable as the current study includes radiation therapy, which is known to be effective against advanced BCC, in combination with vismodegib, also known to have high efficacy against BCC when administered alone.

Sample Size Justification: With accrual of 24 evaluable patients, this test will have 81% power to detect an increase in the overall proportion of patients achieving local-regional control assuming a directional level of significance of 0.10 based upon a one sample exact binomial test. It is anticipated that accrual will be completed in 12-18 months, with each patient treated for approximately 5.5 months and then followed for 12 months after completing protocol therapy. The total study duration is expected to be about 3 years.

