8.5 Analyses Plans

Data will be summarized with respect to demographic and baseline characteristics and safety observations and measurements. The assessment of safety will include calculation of all specified study endpoints (see section 8.2) and will be based mainly on the frequency and attribution of adverse events, the frequency of discontinuation of treatment due to toxicity during concurrent vismodegib plus radiation therapy, and the proportion of patients experiencing Grade

3 or higher AEs related to the treatment components. Adverse events will be summarized by presenting the number and percentage of patients having any adverse event. Any other information collected (e.g. severity or relatedness to study medication) will be listed as appropriate. Toxicities will be tabulated by maximum grade occurring and organ system using the NCI Common Toxicity Criteria version 4.1 during each of 4 protocol stages (vismodegib alone, in combination with radiation therapy, during the immediate 3 months following completion of protocol therapy and then up to 12 months of follow-up after completing treatment).

To evaluate the primary protocol aim the proportion of patients with local-regional control (LRC), those with a CR or PR as defined by RECIST criteria, at 12 months after completing protocol therapy will be calculated and presented with 95% confidence intervals. As a most conservative estimate of disease control any patient beginning concurrent vismodegib and radiation therapy who is removed from study prior to completion of at least 75% of radiation therapy without a documented complete or partial response will be considered as a local-regional failure. To test the primary study hypothesis the observed proportion with LRC will be compared with the null hypothesis of 60% using a one sample test of a binomial proportion.

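### The primary endpoint is set at 12 months from completion of therapy, but tumor visits are timed from a later End of Treatment visit, so none falls at month 12 and no rule names the visit to be used

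*Combined protocol and SAP*

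**What the plan says.** Sections 8.2, 8.3.1 and 8.5 count from the end of therapy:

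- Section 8.2, primary endpoint: "The proportion of patients with local-regional control at 12 months from protocol therapy completion".
- Section 8.3.1: "The alternative hypothesis is that 80% of the patients will obtain local-regional control at 12 months from the end of protocol therapy".
- Section 8.5: the proportion controlled "at 12 months after completing protocol therapy will be calculated and presented with 95% confidence intervals".

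Sections 3.5, 8.1 and 8.3.1 give 12 months of follow-up from completion of therapy. Section 5.5.1 also ends the 12-month follow-up period relative to completion of combination therapy.

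The visit schedule counts from the End of Treatment (EOT) visit:

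- Section 6.1.3, on EOT procedures: "To be completed within 8 – 12 weeks of the last dose of study drug". Table 6.1 agrees, with EOT at weeks 29-33 and the last treatment week at 21.
- Section 6.1.4: "Patients will be followed at 3, 6, and 12 months (+/- 2 weeks) after the End of Treatment visit or until disease progression".
- Abstract, Duration of Follow up: "Follow-up visits will occur at 3, 6, & 12 months (+/- 2 weeks) post End of Treatment visit".
- Table 6.1, first footnote: "Follow-up visits will occur at 3, 6, & 12 months (+/- 2 weeks) post EOT".

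Section 6.1.5 adds survival contacts every 3 months but no tumor assessments. Section 8.5.1 counts failures within a 12-month follow-up period and does not itself state when that period starts.

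**The concern.** The endpoint and the assessments that must supply it use different time origins. No tumor assessment is scheduled at month 12 from completion, and the 2-week visit window is too narrow to reach it. The plan does not define completion of protocol therapy, gives no window for the primary assessment, and names no visit.

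The choice of visit decides which failures count. In a 24-patient trial tested against a fixed cut-off, one patient can change the conclusion. Whichever visit is used, the estimate would be labelled as a 12-month rate without being one.

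**Working it through.** **The plan's own figure.** Inputs from section 8.3.1: n = 24, null 60%, alternative 80%, one-sided 0.10, exact binomial. Requiring at least 18 of 24 controlled gives P(X ≥ 18 | 0.60) = 0.096 and P(X ≥ 18 | 0.80) = 0.811. The stated 81% reproduces.

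**Visit timing.** Section 5.1 plans vismodegib through the end of radiation, so the last dose and the end of radiation coincide. Weeks after completion = EOT offset (8 to 12) + visit time ± 2; months = weeks / 4.348.

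| Assessment | Weeks after completion | Months |
|---|---|---|
| EOT | 8 to 12 | 1.8-2.8 |
| 3 months after EOT | 8+13−2 = 19 to 12+13+2 = 27 | 4.4-6.2 |
| 6 months after EOT | 8+26−2 = 32 to 12+26+2 = 40 | 7.4-9.2 |
| 12 months after EOT | 8+52−2 = 58 to 12+52+2 = 66 | 13.3-15.2 |

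Month 12 lies in the gap between the last two rows. The same anchor leaves the 3-month response endpoint between EOT and the visit labelled 3 months.

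**Variation between patients.** EOT is counted from the last drug dose, but section 5.3 says "any radiation delays are to be stringently avoided, even if drug administration is interrupted". If drug stopped for good at the start of the 7-week radiation course, EOT would fall 1 to 5 weeks after the last fraction. The visit labelled 12 months would then fall at 1+52−2 = 51 to 5+52+2 = 59 weeks after it. Section 8.5.1 keeps such a patient in the efficacy analysis.

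**Size, as an illustration only.** The documents give no failure timing, and section 8.3.1 attaches no time to the 60%. Assume control p of 60% or 80% at month 12, a share f of failures already present at completion, the rest at a constant rate, and no new partial responses after completion. Then S(m) = s0 × (p/s0)^(m/12), with s0 = 1 − f(1 − p). For f = 0.5 and the cut-off of 18:

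| Assessment used | Control if 80% at month 12 | Power | Control if 60% at month 12 | Type I error |
|---|---|---|---|---|
| Month 12 (planned) | 80% | 81% | 60% | 9.6% |
| 58-66 weeks | 79.0-77.5% | 77-72% | 58.1-55.6% | 7-4% |
| 32-40 weeks | 83.7-82.2% | 92-88% | 67-64% | 28-19% |

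At the late visit and the 80% rate, the expected number of patients failing between month 12 and the visit is 24 × (0.800 − 0.790) ≈ 0.2 to 24 × (0.800 − 0.775) ≈ 0.6.

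For f from 0.25 to 0.75, the late visit gives power of 67-79% and type I error of 3-8%. The earlier visit gives type I error of 40-14%. With f = 0, control at the late visit is 0.8^(13.34/12) = 0.780 to 0.8^(15.18/12) = 0.754, and power is 74-63%.

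**The case against.** A reader might infer that the visit 12 months after EOT is obviously the primary assessment, and that the error is therefore merely conservative. The documents do not support stating this flatly. Sections 3.5, 5.5.1 and 8.1 end follow-up 12 months after completion, before that visit takes place. On that reading, the last scheduled assessment inside follow-up is the one at 7.4-9.2 months, which can overstate control at month 12. The conservative direction also depends on there being no new responses. The endpoint is complete or partial response status, so late responses could offset late failures.

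It can fairly be said that sections 3.5, 5.5.1 and 8.1 supply the start that section 8.5.1 omits. That stands as a reading of the follow-up period, but it leaves no tumor assessment at the period's end.

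It can also be said that the shift is small: well under one expected patient of 24 for the late visit in the main illustration. Absence of progression through a later visit also covers month 12. Both points stand and limit the seriousness for the late-visit reading. They do not help if the earlier visit is used.

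The early-stopping scenario is an edge case. For a patient who interrupts and resumes drug, section 5.3 requires the specified number of drug days, which moves the last dose later rather than earlier. This shows why completion needs one definition, but it is not the main point.

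**Conclusion.** The plan contradicts itself on the time origin of its primary endpoint, and nothing in it resolves the contradiction. That conclusion rests only on the stated visit times and the planned coincidence of last dose and end of radiation. It needs no assumption about when failures occur.

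The direction of bias is not determined. The late visit can count failures arising after month 12, which lowers both power and type I error if no new responses occur. Stopping at month 12 leaves the earlier visit, which can inflate type I error. The power and type I figures show plausible size under an assumed failure curve; they are not estimates.

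A reader might also infer that the sample size is wrong. It is not: 24 patients give the stated power for 60% versus 80%. What is unsettled is whether the observed proportion will be measured at the time to which the 80% refers. This should be corrected before the primary analysis.

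**What to change.** Use one time origin throughout.

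**Preferred.** Time the follow-up tumor visits from the last day of protocol therapy, defined once, for example as the later of the last vismodegib dose and the last radiation fraction. The 12-month visit then falls at 50 to 54 weeks and contains the endpoint time. In the same illustration (f = 0.5), control at the 80% rate is 80.4-79.7% and power 82-80%.

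**Alternative.** Keep the schedule, define the primary time point as the visit 12 months after EOT, and count failures up to and including it. Restate sections 8.2, 8.3.1 (both the 60% and the 80%) and 8.5 at that time. If both rates are restated from the illustration, 24 patients still give 77% power (58.1% versus 79.0%, at least 18) to 85% (55.6% versus 77.5%, at least 17).

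**In either case.** Name the visit and window for the primary assessment in section 8.5, and state in section 8.5.1 when the 12-month period starts. Align the Abstract, sections 3.5, 5.5.1, 6.1.3, 6.1.4 and 8.1, and Table 6.1. Time the 3-month RECIST assessment from the same origin. Relabelling the current EOT visit as month 3 would repeat the fault, because it falls at 1.8-2.8 months.

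**Cost.** Either option is a protocol amendment. The first moves post-treatment imaging about 2-3 months earlier. The second lengthens stated follow-up by about 2-3 months and needs both rates justified at the later time.

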6.1.5 Long Term/Survival Follow-up Procedures

The study team will follow patients for survival outcome via telephone calls or medical record requests approximately every 3 months for 12 months, until death or loss to follow-up, whichever occurs first. Additional, survival follow-up information may be collected via telephone calls and/or at clinic visits every 3 months for 12 months. Follow-up may consist of at least a telephone contact with the patient, a family member, or physician to inquire about the patient's survival status.

If/when a subject begins a new type of non-protocol treatment for laBCC or mBCC, long-term follow up may cease. Subjects will continue to be followed if they have not recurred local-regionally within the original treated PTV. If they have a BCC in a non-treated separate location, or if metastatic disease occurs, subjects will continue to be followed for the local-regional disease control outcomes. Subjects would be taken off protocol if they have any form of non-protocol treatment affecting the primary local or nodal site that was originally treated or if they receive vismodegib or other Hedgehog inhibitor or chemotherapy outside of original protocol parameters. Patients off study protocol who need to have vismodegib will not have drug provided by the study.

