2.3.2 Secondary Endpoints

- Estimate of the probability of PFS, with failure defined as any disease recurrence or death due to any cause, and OS with each duration measured from the time of first treatment with vismodegib to 12 months after completion of study treatment.
- The number and attribution of all adverse events, (including vital signs, physical findings, and clinical laboratory results, CTCAE, v 4.0) in patients who receive any amount of study drug and radiation therapy at any point during protocol therapy or during the followup period.
- The proportion of any adverse events (CTCAE, v. 4.0) assessed to be definitely, probably, or possibly related to vismodegib or its combination with radiation therapy at any point during protocol therapy or during the followup period.
- The proportion of patients experiencing Grade 4-5 adverse events assessed to be definitely, probably, or possibly related to the induction or concurrent treatment components of the protocol regimen (that is not definitely related to disease progression) at any point during protocol therapy or during the followup period.
- The proportion of patients discontinuing treatment due to toxicity during the concurrent administration of vismodegib and radiation therapy (<75% of planned radiation therapy delivered).
- Response rate (as per RECIST) of the primary site and regionally involved areas following all treatment components at 3 months after the completion of protocol therapy.

- Proportion of patients with a decrease of BCC within the irradiated planning tumor volumes (PTV) in patients who complete initial combined therapy, indicating a clinical response to vismodegib and radiation therapy.

3 Study Design

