3.5 Duration of Follow Up

Patients will be followed for 12 months after completion of all protocol therapy, or until death, whichever occurs first. Patients removed from study for unacceptable treatment related adverse event(s) will be followed until resolution or stabilization of all treatment related adverse events to Grade 2 or lower.

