7.1 Evaluation of Efficacy (or Activity)

A new cutaneous BCC will be considered as progressive local-regional disease (locally or regionally relapsed) if the lesion is > 5 mm, within the PTVs, and can be clearly documented as not being previously present. The new lesion should be biopsied but will be considered as PD unless confirmed on biopsy not to be consistent with BCC. If the new cutaneous lesion is not biopsied or the histology is inconclusive, it should be considered to be BCC and indicative of PD. Significant enlargement of a cutaneous BCC that was present at baseline should also be considered as PD.

If imaging shows a high likelihood of distant metastases (investigators are highly encouraged to contact one of the Principal Investigators with any questions in this matter), ongoing protocol-prescribed therapy may be terminated based on evaluation of potential clinical benefits versus risks to the patient, as assessed by the study investigator. The patient may still be eligible for follow-up, per stipulations in section 6.1.5. New distant metastatic lesions should be biopsied if possible and will be considered as PD unless confirmed on biopsy not to be consistent with BCC. If the new metastatic lesion is not biopsied or the histology is inconclusive, it should be considered to be indicative of PD.

Note: Information about patients who have progressed on study and been removed from study may be voluntarily submitted at the discretion of the treating investigator (see Section 6.1.5).

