The secondary clinical aims of the duration of progression free survival (PFS) and overall survival (OS) will be measured from the start of protocol therapy until death due to any cause or until the first evidence of any disease progression, or death, respectively. Point estimates (e.g. median, percent PFS at 12 months) with 95% confidence intervals will be calculated using the Kaplan-Meier product limit method to summarize results. Based upon RECIST criteria, the proportion of patients responding in the primary site and regionally involved areas at 3 months after completing protocol therapy will be determined and presented with 95% confidence intervals. The proportion of patients achieving any decrease in BCC within the boundaries of the treated radiation PTV area will be determined and presented with a 95% confidence interval. In addition, the proportion of patients who start concurrent vismodegib and radiation therapy and receive at least 75% of the planned radiation therapy will be determined and presented with a 95% confidence interval to summarize the feasibility of administering concomitant therapy.

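### Survival follow-up is required in some sections but optional or ended after treatment failure in others, so overall survival may be overestimated

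*Combined protocol and SAP*

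**What the plan says.** **The endpoint.** Section 2.3.2 lists "OS with each duration measured from the time of first treatment with vismodegib to 12 months after completion of study treatment". Section 8.5 says the PFS and OS estimates, with 95% confidence intervals, will be "calculated using the Kaplan-Meier product limit method to summarize results". Section 8 states no censoring rule for OS.

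**Text that requires follow-up.**
- Section 3.5: "Patients will be followed for 12 months after completion of all protocol therapy, or until death, whichever occurs first". It makes no exception for progression or new therapy.
- Section 6.1.5, first sentence: "The study team will follow patients for survival outcome via telephone calls or medical record requests approximately every 3 months for 12 months". The only earlier ends that this sentence allows are the patient's death and losing contact. A telephone contact with a relative or physician is enough.

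**Text that makes follow-up optional or ends it.**
- Section 6.1.5, second paragraph: when a subject "begins a new type of non-protocol treatment for laBCC or mBCC, long-term follow up may cease". The next sentence reads "Subjects will continue to be followed if they have not recurred local-regionally within the original treated PTV". For patients with metastatic disease or a BCC elsewhere, follow-up continues, but only local-regional outcomes are named.
- Section 7.1: information on patients who progressed and were removed "may be voluntarily submitted at the discretion of the treating investigator", with a pointer back to 6.1.5.
- Section 6.1.2.2: patients who progress during induction leave the study.
- Section 6.1.3: salvage surgery means discontinuation, and later follow-up is optional and needs a separate consent.
- Section 6.1.4: clinic visits stop at progression.
- Table 6.1, footnote on follow-up visits: collection of survival information is worded as optional.

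**The concern.** Kaplan-Meier treats a censored patient as having the same future risk of death as patients still under observation at that time. Nearly all the exits listed above are tied to progression or to its treatment. If sites use them, the patients who drop out of the OS risk set will tend to have the worse prognosis, their later deaths will not be counted, and the curve will sit too high.

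Because stopping is left to discretion, the extent of loss may also differ between sites. With 24 patients and few expected deaths, a small number of missed deaths can dominate the OS result. At stake is a stated secondary endpoint. It is descriptive, with no hypothesis test or decision rule attached.

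**Working it through.** **Step 1. The plan's own figure.** No OS assumption is stated. The only power figure is for the primary endpoint (section 8.3.1): 24 evaluable patients, 60% versus 80% local-regional control, one-sided 0.10, exact binomial, 81% power. With success at 18 or more of 24:
- P(X ≥ 18 | 24, 0.60) = 0.096
- P(X ≥ 18 | 24, 0.80) = 0.811

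A cut-off of 17 gives a type I error of 0.192, so 18 is the design's rule and 81% reproduces. This test does not use OS and is not affected.

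**Step 2. How many patients could be exposed.** At the design rates, 20% to 40% are not controlled:
- 24 × 0.20 = 4.8, about 5
- 24 × 0.40 = 9.6, about 10

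At those rates this is an upper bound on the number of uncontrolled patients who switch treatment early. It includes stable disease and failures first seen at the last assessment.

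**Step 3. Bounds on OS.** Let k patients have unknown vital status and suppose no other death occurs. OS then lies between (24 − k)/24 and 1:
- k = 5: 19/24 = 79% to 100%
- k = 10: 14/24 = 58% to 100%
- one missed death: 1/24 = 4.2 points

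**Step 4. Direction and possible size of the bias.** A simulation of 200,000 patients per scenario estimated OS at 17 months (about 21 weeks of therapy plus 12 months). Failure times were uniform over months 5 to 14. Deaths in failing patients all came after failure. Either half or all of the failing patients were censored at failure. The death rates are assumptions.

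| Uncontrolled | Deaths by month 17, failing / non-failing | True OS | Bias, half censored | Bias, all censored |
|---|---|---|---|---|
| 20% | 5% / 5% | 95.0% | +0.3 | +0.6 |
| 20% | 10% / 2% | 96.4% | +0.8 | +1.9 |
| 20% | 20% / 2% | 94.4% | +1.7 | +3.8 |
| 20% | 30% / 5% | 90.1% | +2.5 | +5.5 |
| 40% | 5% / 5% | 95.0% | +0.5 | +1.2 |
| 40% | 10% / 2% | 94.8% | +1.5 | +3.7 |
| 40% | 20% / 2% | 90.7% | +3.1 | +7.7 |
| 40% | 30% / 5% | 85.0% | +4.4 | +11.2 |

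The bias, in percentage points, is upward in every scenario. With complete vital status this source of bias disappears.

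**Step 5. A rough anchor for deaths.** Section 1.2.2 reports 7 deaths among 104 patients in the earlier phase II vismodegib trial: 7/104 × 24 = 1.6 per 24. That trial included metastatic disease, so this is only an order of magnitude.

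**The case against.** The strongest reply is that the required schedule already exists. The first sentence of 6.1.5 commits the team to survival follow-up until death or loss, and section 3.5 says much the same. The later permission is only a permission. Its trigger is new non-protocol treatment, not failure: a failing patient without new therapy is not covered, and a patient treated for a BCC elsewhere could be. This stands, and it limits the claim to a possible, preferential loss.

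A reader might go further and infer that OS is censored in exactly the patients who fail. The documents do not support that, for the reasons just given and because 6.1.5 keeps patients with distant-only disease in follow-up. That protection is incomplete, since section 6.1.6 lists distant progression as a reason for withdrawal.

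A reader might also infer that Kaplan-Meier would show 100% when true OS is 88% to 96% (21/24 to 23/24, that is, 3 to 1 deaths). This needs every death to follow a switch, every switch to end follow-up, and no other death. The documents give no such death count. Section 3.3.2 excludes distant metastasis and life expectancy under one year, and section 5.5.1 places standard treatment for recurrence after the 12-month follow-up.

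Deaths also have a second route. Section 7.4 covers all deaths in safety reporting, and 7.5.2.3 makes death a serious event. This is a partial backstop: the window in 7.4 closes at study discontinuation if that comes first, and a Table 6.1 footnote gives 90 days after the last dose.

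Finally, the OS interval will be wide. The exact 95% interval for 24 of 24 has a lower limit of 0.025^(1/24) = 85.8%. Imprecision does not excuse an avoidable bias, but it keeps the point in proportion.

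**Conclusion.** The concern holds as an inconsistency with a predictable direction of bias. Some sections require survival follow-up; others make it optional or end it after new treatment, progression or salvage surgery. A site that follows the second group of passages can lose vital status preferentially in failing patients, and the Kaplan-Meier OS estimate would then tend to be too high.

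The size cannot be derived from the documents. The bounds of 79% to 100% (5 unknown) and 58% to 100% (10 unknown) assume that all uncontrolled patients at the design rates are lost and that nobody else dies. The simulated +0.3 to +11.2 points rest on assumed death rates and on half or all failing patients being censored at failure.

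Section 6.1.2.2 matters for OS only if OS is reported for all treated patients. The efficacy population in 8.5.1 begins with patients who start radiation, and the plan does not name a separate OS population.

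The effect is confined to a secondary, untested estimate. The correction is a cheap improvement and worth making.

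**What to change.** 1. **Section 6.1.5.** State that vital status is collected about every 3 months until 12 months after therapy for every treated patient, regardless of progression, removal from protocol or later treatment, unless consent is withdrawn. Limit the permission to stop follow-up to tumor assessments after in-PTV failure or new treatment of the treated site.
2. **Section 7.1.** Exempt vital status from the voluntary-submission note.
3. **Sections 6.1.2.2 and 6.1.3 and the Table 6.1 footnote.** Align them, so that leaving the study or having salvage surgery does not end vital-status collection and the footnote no longer reads as optional.
4. **Section 8.5.** Censor OS only at the date last known alive, name the OS population, and report the number of patients with unknown vital status. A worst-case sensitivity analysis that counts those patients as deaths would show how much the result depends on them.

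**Cost.** At most four contacts each for roughly 5 to 10 patients (4 × 5 = 20 to 4 × 10 = 40 calls), within a call schedule already planned. The consent form may need a wording change so that vital status after salvage surgery does not depend on separate consent. Under section 9.4 the amendment needs approval by the Protocol Review Committee and the IRB. The sample size, the primary analysis and patient treatment do not change.
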